7.3. Confidentiality

A site and participant number will be assigned for each participant. The database will only be identified by participant number and will not contain any personal identifiers. The results of all assessments will be kept strictly confidential unless an appropriate written release of information is provided by the participant and/or parent(s)/legal guardian.

The research team will do everything possible to keep others from learning about the participant's involvement in this research study. Each participant will be assigned a sequential identification number, and these numbers, rather than names, will be used to collect, store, and report participant information.

Data from this study may be submitted to the National Database for Autism Research (NDAR). NDAR is a computer system run by the National Institutes of Health that allows researchers studying autism to collect and share information with each other. During and after the study, the researchers will send information about your health and behavior, to NDAR. Before sending data to NDAR, however, information such as name, address, and phone number, will be removed and replaced with a code number. Other researchers nationwide can then file an application with the National Institutes of Health to obtain access to your study data for research purposes. Experts at the National Institutes of Health who protect health and science information will look at every request carefully to minimize risks to your privacy.

Data from this study will be shared with collaborators at Northwestern and Eotvos Lorand University in Hungary working on developing assessment tools designed to reduce time, burden and improve detailed analysis of treatment effects from this treatment.

8. Safety Reporting

8.1. Adverse Events (AEs).

ICH E6 defines an AE as any untoward medical occurrence in a patient or clinical investigation subject administered a pharmaceutical product regardless of its causal relationship to the study treatment. An AE can therefore be any unfavorable and unintended sign (including an abnormal laboratory finding that is not directly obtained for purposes of the study), symptom, or disease temporally associated with the use of medicinal (investigational) product. The occurrence of an AE may come to the attention of study personnel during study visits and interviews of a study subject presenting for medical care, or upon review by a study monitor. All AEs including will be captured on the appropriate source documentation, the structured AE rating form. Information to be collected includes event description and clinician's assessment of severity.

8.2. Treatment Emergent Adverse Events (TEAEs).

Safety analysis will focus on TEAEs. Medical and behavioral conditions will be evaluated at screening and baseline, and will only be considered TEAEs if the severity increases significantly after a participant has completed a treatment session. All TEAEs will be documented during the course of the study regardless of relationship to treatment. All TEAEs will be followed to adequate resolution. If a TEAE is also a serious adverse event (SAE) and/or Unexpected Problem (UP), the SAE or UP forms will also be completed. If a TEAE is both a SAE and UP, only the SAE form and the AE FORM will be completed.

8.3. *Suicidality Assessment.*

Suicidality assessments will be completed for each participant during visits with Study clinicians. The clinician will determine if the participant understands the concept of death and making one's self die or hurt. If the participant is able to understand these concepts, they will be asked if they have any thoughts about wanting to die, wanting to hurt themselves, wanting to kill themselves, and if s/he has done anything to hurt himself/herself so s/he would die or have done anything to hurt himself/herself for any other reason. If the participant is deemed not to understand these concepts, his/her caregiver will be asked the above questions. The caregiver will also be asked to rate if this is a significant changes in severity or frequency from the participant's behavior at baseline.

8.4. Safety Reporting

The Study clinician will discuss events with the patient and caregiver; review the participant's history of any similar behaviors or suicidal ideation, and the caregiver's perception of any change in severity of frequency of the behavior. S/he will review alarm values of labs and ECGs and serious adverse events within 3 working days of their reporting and who will review all new treatment emergent adverse effects of moderate or greater severity three times a year prior to DSMB meetings. Cases may also be reviewed by the DSMB.

8.5. Adverse Event Ratings

Serious Adverse Events (SAE).

An SAE is defined as an AE that meets one of the following conditions:

- Death during the period of protocol-defined surveillance
- Life-threatening event (defined as a subject at immediate risk of death at the time of the event)
- An event requiring inpatient hospitalization or prolongation of existing hospitalization during the period of protocol defined surveillance
- Results in congenital anomaly or birth defect
- Results in a persistent or significant disability/incapacity
- Any other important medical event that may not result in death, be life threatening, or require hospitalization, may be considered a serious adverse experience when, based upon appropriate medical judgment, requires medical or surgical intervention to prevent one of the outcomes listed above. Examples of such medical events include allergic bronchospasm requiring intensive treatment in

Confidential

Rush University Medical Center

an emergency room, blood dyscrasias or new onset of convulsions that do not result in inpatient hospitalization.

All SAEs will be:

- recorded on the appropriate SAE CRF
- followed through resolution by a study clinician
- reviewed and evaluated by a study clinician

Unanticipated Problems (UP). We will consider unanticipated problems involving risks to subjects or others to include, in general, any incident, experience, or outcome that meets all of the following criteria:

- unexpected (in terms of nature, severity, or frequency) given (a) the research procedures that are described in the protocol-related documents, such as the IRB-approved research protocol and informed consent document; and (b) the characteristics of the subject population being studied;
- related or possibly related to participation in the research (in the guidance document, possibly related means there is a reasonable possibility that the incident, experience, or outcome may have been caused by the procedures involved in the research); and
- suggests that the research places subjects or others at a greater risk of harm (including physical, psychological, economic, or social harm) than was previously known or recognized.

Severity of Event. All AEs will be rated by the Study clinician using a protocol defined grading system. For events not included in the grading system, the following guidelines will be used to quantify intensity.

- Mild*: events require minimal or no treatment and do not interfere with the subject's daily activities.
- Moderate*: events result in a low level of inconvenience or concern with the therapeutic measures. Moderate events may cause some interference with functioning.
- Severe*: events interrupt a subject's usual daily activity and may require systemic drug therapy or other treatment. Severe events are usually incapacitating.
- Life-threatening*: Substantial risk dying or requires intervention to prevent death.
- Death related to AE*: Subject died as a result of the event, self-explanatory.

Changes in the severity of an AE will be documented to allow an assessment of the duration of the event at each level of intensity to be performed. Adverse events characterized as intermittent require documentation of onset and duration of each episode.

Relationship to Study Treatment. Study clinicians will assess and document whether the AE is related to treatment condition. However, the relationship to study treatment will not be a factor in determining whether or not an AE is reported in this study. If there is any doubt as to whether a clinical observation is an AE, the event will be reported. All AEs must have their relationship to study product assessed using the terms: associated or not associated. In a clinical trial, the study product must always be suspect. To help assess, the following guidelines are used.

- Certain*: The adverse event and administration of the study drug are related in time, and a direct association can be demonstrated.
- Probably*: The adverse event and administration of the study drug are reasonably related in time, and the adverse event is more likely explained by the study drug than other causes.
- Possible*: The adverse event and administration of the study drug are reasonably related in time, and the adverse event can be explained equally well by causes other than the study drug.

Confidential

Rush University Medical Center

- *Unrelated*: The adverse event is clearly explained by another cause not related to the study drug.
- *Unknown or not applicable*

Reporting Procedures: Serious Adverse Events & Unanticipated Problems

Any AE considered serious by the PI or Sub-Investigator (Sub-I) or which meets the aforementioned criteria must be submitted on an SAE form to the Rush IRB. Additionally, any event which meets the aforementioned criteria for an unanticipated problem also needs to be reported to the Rush IRB. It should be reported to the following numbers. It is preferable to have a written report (fax or email) for documentation purposes.

IRB Contact Information:

Research and Clinical Trials Administration
[name]
[name]

IRB [contact]
IRB [contact]

The study clinician will complete and submit an SAE or a UP Form within the following timelines:

- All deaths and immediately life-threatening events, whether related or unrelated, will be recorded on the Serious Adverse Event Form and sent by fax to the medical monitor within 7 business days of site awareness.
- Serious adverse events other than death and immediately life-threatening events, regardless of relationship, will be reported by fax within 7 business days of site awareness. The study clinician will complete and submit SAE and UE forms within 7 business days.
- Unanticipated problems involving risk to subjects and subject complaints will be reported to the Rush IRB within 10 days of site awareness.
- Other supporting documentation of the event may be requested and should be provided as soon as possible. All SAEs will be followed until satisfactory resolution or until the PI or Sub-Investigator deems the event to be chronic or the patient to be stable.

Reporting to Other Regulatory Bodies

- Medical Monitor: The study team will report all SAEs, UPs, and other reportable events to the medical monitor within 14 days and receive acknowledgement that she has reviewed them.
- DSMB: The study team will report SAEs, Ups, and other reportable events that are considered possibly related to the study treatment to the DSMB within 14 days of being made aware of their occurrence.
- FDA: If the event meets FDA reporting criteria (below), the IND holder or investigator will follow specified reporting procedures. Reportable events will meet the following criteria:
 - Suspected Adverse Reaction: meaning there is reasonable probability that the drug caused the event. Meaning there is evidence to suggest a causal relationship between the drug and adverse event.
 - Serious (see section above for definition)
 - Unexpected (see section above for definition)

Timelines for reporting to the FDA

- Unanticipated fatal or life threatening adverse events (7 days)
- Unanticipated non-fatal/non-life threatening events (14 days)

Other reportable events

Other reportable will be reported during the annual review. Other reportable events with shorter reporting intervals include pregnancy of subject or the subject's sexual partner and serious intentional self-harm or serious suicidal ideation.

- In case of a pregnancy, investigators will follow the pregnancy until completing (either termination or birth). The baby will be followed until s/he is 1 month old to assess and record any medical complications. The initial report will be sent to the IRB within 7 days of the study team's awareness.
- In case of serious intentional self-harm or serious suicidal ideation, the physician/clinician should take necessary steps to ensure the safety of the participant including involuntary hospitalization (if needed). This should be reported (on the appropriate source document) to the IRB within 7 days of the study team's awareness.

Stopping procedures.

Subjects may be withdrawn from the study for any of the following reasons:

- At the participant or guardian's request
- If moderate or severe AEs occur that cannot be addressed by the PI, Study clinician or medical monitor
- If a subject is worsening clinically (i.e. have CGI-I = 6 (much worse) or 7 (much worse)) and there has been a return visit/call within 1-2 weeks to revisit/re-evaluate the CGI-I. If subject remains at a CGI-I = 6 or 7, the case can be discussed with the medical monitor to get approval for the participant to continue
- Study noncompliance
- Study physician/clinician discretion

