8.8. Statistical analysis

Specific Aim 1 & Exploratory Aim 1: Safety and tolerability will be analyzed by analyzing for group differences on total scores and domains of the AE form and satisfaction surveys respectively. Efficacy analysis will be follow analytic procedures used to derive social behavior and social cognition composites for the Seaver-NETT RCT¹⁶. First, a principal components analysis with varimax (orthogonal) rotation will be conducted on subscales of the primary social behavior measures - Griffith Empathy Scale and CCC-2; and raw total scores on primary social cognition outcomes – RMET and DANVA2. The PCA is used to develop composite scores in a field with no viable outcomes for higher-order core social impairments as well as to minimize floor and ceiling artifacts, effects of variability in response, and other sources of measurement error. Variables with high factor loadings for subscales will be entered into composite score development for the social cognition and social behavior composites. Missing, invalid, and/or incomplete data (i.e. more than 30% items missing when not pre-defined by scale) will be excluded from the factor analysis.

A linear mixed model analysis will be conducted on all participants with at least two of four available time points (Wk 0, Wk 12, 1-mon, 3-mo). Composite scores of co-primary outcomes social behavior and social cognition will be used as the response variable; treatment condition, time, and condition * time interactions will be covariates. Verbal IQ will also be entered into the model in exploratory moderator analyses. We will estimate effect sizes (Cohen's d) and confidence intervals (95%) acknowledging the likelihood that analyses may not permit definitive conclusions given the likely size of the confidence intervals.

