Official title: Integrated Oxytocin and Nonverbal, Emotion Recognition, and Theory of Mind

Training for Children With Autism Spectrum Disorder

NCT number: NCT02918864

Document date: 2/8/2021

Statistical Analysis Plan

Data Reduction and Outcome Variables. Safety and tolerability will be evaluated by comparing group differences on total counts and domains of the AE form and ratings on parent satisfaction surveys respectively. Efficacy analysis will follow analytic procedures used to derive social behavior impairment (SBI) and social cognition (SC) composites for the Seaver-NETT RCT16. First, principal components analysis (PCA) with promax rotation will be conducted on the primary social behavior impairment measures, the Nonverbal Communication and Social Relations subscales of the Children's Communication Checklist-2 (CCC-2) and the total score of the Griffith Empathy Scale (GEM). A separate PCA will be conducted on the primary social cognition outcomes, the Reading the Mind in the Eyes Test (RMET) and Diagnostic Analysis of Nonverbal Accuracy-2 (DANVA-2). The PCAs are used to confirm that these measures contribute to previously identified constructs in a field with no viable outcomes for higher-order core social impairments as well as to minimize floor and ceiling artifacts, effects of variability in response, and other sources of measurement error.

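### Adverse events are graded for severity, but the planned between-arm safety comparison does not use the grade, so an excess of moderate-or-worse events on oxytocin can be diluted by mild ones

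*Protocol*

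**What the plan says.** **What is collected.** Section 8.1 has severity recorded for every event: "Information to be collected includes event description and clinician's assessment of severity". Section 8.5 gives a guideline scale from mild to death for events outside the protocol's own grading system. It also asks that shifts in grade be followed ("Changes in the severity of an AE will be documented to allow an assessment of the duration of the event", at each level of intensity), and adds "Adverse events characterized as intermittent require documentation of onset and duration of each episode".

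**Where grade is used.** Section 8.2 states "Safety analysis will focus on TEAEs"; a condition present at screening or baseline enters only if it worsens significantly. Section 8.4 has the study clinician "review all new treatment emergent adverse effects of moderate or greater severity" three times a year, before DSMB meetings. Section 8.5 (Stopping procedures) lists moderate or severe events that cannot be addressed among the reasons for withdrawal.

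**What is compared between arms.** The SAP (Data Reduction and Outcome Variables): "Safety and tolerability will be evaluated by comparing group differences on total counts and domains of the AE form". Protocol Section 8.8: "analyzing for group differences on total scores and domains of the AE form". One document has counts and the other scores, and no scoring rule is given. Neither names a test, says whether the unit is the child, the event or the episode, or plans a table by grade.

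**The concern.** Safety and tolerability are part (A) of the primary aim (Section 2.1). Section 8.9 calls the trial potentially underpowered and justifies it partly by the safety information it will yield. The background (Section 1) reports mild to moderate side effects in the pilot, so both levels are to be expected, and a total merges them.

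If mild events are frequent and similar in the two arms, they add variance to the total and nothing to the difference. An excess of moderate-or-worse events, the level that Section 8.4 singles out for review, could then be hard to see in the one comparison the SAP specifies. The data that would show it directly are collected, but no analysis of them is planned.

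**Working it through.** The plan states no power or sample size for safety, so there is no figure of its own to reproduce.

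**Inputs from the documents**
- 24 per arm: 25 per group less 5% attrition, 25 × 0.95 = 23.75 (Section 8.9).
- 35 per arm: Phase 2, 70/2 (Section 3.1).
- 40 per arm: 80/2 (Section 2.1).
- 45 per arm: 90/2 (Section 3.5).

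**Assumptions, because the documents give no AE rates**
- Moderate-or-worse events per child: Poisson, mean 0.2 on control and 0.6 on ION-ASD.
- Mild events per child: mean 1.5 to 4, equal in both arms, Poisson or overdispersed (negative binomial).
- Tests at two-sided 5%: Welch t on total counts, and Fisher's exact test on children with at least one moderate-or-worse event. The plan names neither; they stand in for the two kinds of summary.

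**Step 1. Proportions of children affected.** 1 − exp(−0.2) = 18.1% and 1 − exp(−0.6) = 45.1%.

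**Step 2. Why the total dilutes.** The difference in mean total is 0.6 − 0.2 = 0.4 whatever the mild rate, but the standard error grows with it. With Poisson counts, SE = √[(λ₀ + λ₁)/n] and power ≈ Φ(0.4/SE − 1.96) + Φ(−0.4/SE − 1.96).
- Mild mean 3, n = 24: SE = √[(3.2 + 3.6)/24] = 0.532; 0.4/0.532 = 0.75; power ≈ 12%.
- Mild mean 1.5, n = 45: SE = √[(1.7 + 2.1)/45] = 0.291; 0.4/0.291 = 1.38; power ≈ 28%.
- Moderate-or-worse events alone, n = 24: SE = √[(0.2 + 0.6)/24] = 0.183; 0.4/0.183 = 2.19; power ≈ 59%.

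**Step 3. Simulated power, 0.2 versus 0.6, equal mild rates**

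| Comparison | 24 per arm | 35 per arm | 45 per arm |
|---|---|---|---|
| Total count, Poisson mild mean 1.5 | 17% | 22% | 27-28% |
| Total count, Poisson mild mean 3 | 12% | 14% | 18% |
| Any moderate-or-worse event, Fisher | about 42% | about 60% | about 74% |

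With overdispersed mild counts the total-count test falls as low as about 5%. Over all settings it has about 5-28%, against about 42-75% for Fisher's test.

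**Step 4. How far this depends on the assumptions**
- *Mild events also rise 1.5-fold on ION-ASD (3 to 4.5 per child):* total-count power is about 88%, 97% and 99% at 24, 35 and 45 per arm with Poisson counts, and about 31-56% over the same sizes if overdispersed.
- *Moderate-or-worse events common (0.5 versus 1.5, Poisson mild mean 1):* total-count power is about 67% at 24 and 92% at 45 per arm.
- *Total is a score, with a moderate-or-worse event scored 2 or 3 and a mild event 1 (Poisson mild mean 3):* about 23-41% or 35-60%, compared with 12-18% for the plain count.
- *Wider grid of 90 settings* (24, 35 or 40 per arm; mild mean 1, 3 or 5; control rate 0.1 to 1.0, tripled; Poisson or overdispersed): total-count power is under 50% in 67. It is 5-33% at control rates of 0.2 or less and 7-55% at 0.3.
- *Control rate 0.1 in that grid:* Fisher's test itself has only 19-40%.
- *Control rate 1.0, Poisson mild mean 3, 24 per arm:* Fisher's test has 77%, below the 87% of the total count.

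**The case against.** The strongest case against is that any power figure here rests on rates the documents do not contain. A reader might infer that a tripling of moderate-or-worse events would usually be missed. The documents do not support that as a general statement: Step 4 shows the total-count test doing well when such events are common, or when mild events rise too. The latter is plausible, since Section 1 lists nasal irritation, runny nose and tearing among possible effects. At 24 per arm the grade-based test also falls short of 50% in the main scenario. All of this stands, and it is why the size is given as conditional and the remedy as an estimate.

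A reader might also infer that the plan ignores severity. It does not. Grade enters the definition of a treatment-emergent event, the periodic review and the withdrawal reasons, and the DSMB monitors non-serious events on an ongoing basis (Section 8.6). A cluster of worse events could be noticed that way. But none of these is described as a comparison between arms.

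Three further points narrow the concern without removing it:
- Domains are compared as well as totals, and the simulation covers only the total. Nothing in either document says that the domains separate grades.
- The protocol's score may be weighted by grade. That would recover part of the loss, but the scoring is undefined and the SAP has counts.
- It is tempting to say that a recurring mild symptom adds many counts. Section 8.5 requires each episode of an intermittent event to be documented; it does not say that each episode is counted separately.

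Section 8.5 itself contains no error. The gap is in the SAP's safety sentence.

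**Conclusion.** The point holds in a limited form. Severity is recorded and tracked, safety is part of the primary aim, and neither document plans a between-arm comparison by grade. A total count weights all grades equally and can dilute an excess of moderate-or-worse events.

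Under the assumed rates in Step 3 the dilution is large, but the figures depend on three things that the documents leave open: how common moderate-or-worse events are, whether mild events differ between arms, and how a total is formed. The conclusion that grade should be tabulated by arm needs none of these rates. It follows from what is collected and what is planned. This is an improvement that should be made, not a flaw that invalidates the safety assessment.

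**What to change.** In the SAP's safety paragraph:

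1. Tabulate each child's worst treatment-emergent grade by arm, one entry per child however many episodes occurred.
2. Report the number of children with at least one moderate-or-worse treatment-emergent event by arm, overall and by AE-form domain, with a risk difference and 95% CI. Present it as an estimate rather than relying on a p-value, since power is low at these sample sizes when events are uncommon.
3. Keep total counts as a description, and state the counting unit.
4. Reconcile the protocol's score totals (Section 8.8) with the SAP's count totals. If a score is meant, give the scoring rule.

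The cost is a few sentences and one more table from grades already collected. The downside is one more safety comparison to interpret. No clinical procedure changes.
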